### **Prior/Concurrent Clinical Study Experience**

12. Participation in the study would result in loss of blood or blood products in excess of 500 mL within 3 months.
13. Current enrolment in any clinical study involving an investigational study intervention or any other type of medical research.
14. Current enrolment or past participation in this study.

### **Diagnostic assessments**

15. Presence of Hepatitis B surface antigen (HBsAg) or hepatitis B core antibody (HbcAb) at screening or within 3 months before the first challenge day.
16. Positive Hepatitis C antibody test result at screening or within 3 months before the first challenge day.

NOTE: Subjects with positive Hepatitis C antibody due to prior resolved disease can be enrolled, only if a confirmatory negative Hepatitis C RNA test is obtained

17. Positive Hepatitis C RNA test result at screening or within 3 months before the first challenge day.

NOTE: Test is optional and subjects with negative Hepatitis C antibody test are not required to also undergo Hepatitis C RNA testing

18. Positive pre-study drug/alcohol screen.
19. Positive human immunodeficiency virus (HIV) antibody test at screening or within 3 months before the first challenge day.
20. Current use of known drugs of abuse.

### **Other Exclusions**

21. Participants who present with damaged skin including sunburn, scar tissue, moles, uneven skin tones and dark skin tone (Fitzpatrick>2), tattoos, body piercings, branding or other skin disfigurement on or near the intended site of application which could interfere with the assessments.
22. Regular alcohol consumption within 6 months before the study defined as an average weekly intake of >21 units for males or >14 units for females. One unit is equivalent to 8 g of alcohol: a half-pint (~240 mL) of beer, 1 glass (125 mL) of wine or 1 (25 mL) measure of spirits.
23. Smoking test result indicative of smoking, history or regular use of tobacco- or nicotine-containing products (e.g. nicotine patches or vaporizing devices) within 6 months prior to screening.
24. Sensitivity to any of the study interventions, or components thereof, or drug or other allergy that, in the opinion of the investigator or medical monitor, contraindicates participation in the study.
25. Unable to refrain from the use of topical medications from before the first to after the last challenge visit.

### **5.3. Lifestyle Considerations**

Not applicable.

#### **5.3.1. Caffeine, Alcohol, and Tobacco**

- During each visit, participants will abstain from ingesting caffeine- or xanthine-containing products (e.g., coffee, tea, cola drinks, and chocolate).
- Participants will abstain from alcohol for 24 hours before each visit.
- Only non-smokers are allowed to participate in this study, therefore the use of tobacco products will not be allowed during the study.

### **5.3.2. Activity**

- Participants will abstain from strenuous exercise for 48 hours before each blood collection for clinical laboratory tests. Participants may participate in light recreational activities during studies (e.g., watching television, reading).

### **5.4. Screen Failures**

Screen failures are defined as participants who consent to participate in the clinical study but are not subsequently entered in the study. A minimal set of screen failure information is required to ensure transparent reporting of screen failure participants to meet the Consolidated Standards of Reporting Trials (CONSORT) publishing requirements and to respond to queries from regulatory authorities. Minimal information includes demography, screen failure details, eligibility criteria, any protocol deviations and any serious adverse events (SAEs).

Individuals who do not meet the criteria for participation in this study (screen failure) may be rescreened only once after consultation and on approval of the GSK Medical Monitor. Rescreened participants should be assigned a new participant number. In the event of out -of -range results of safety results, the test maybe repeated once within the screening window without this being considered a rescreen. If a retest result is again outside the reference range and considered clinically significant by the investigator and GSK medical monitor, the participant will be considered a screen failure.

Individuals who meet the eligibility criteria and are reserve participants who are subsequently not required may also be rescreened for a start date later in the study.

## **6. STUDY INTERVENTION AND CONCOMITANT THERAPY**

Study intervention is defined as any investigational intervention(s), marketed product(s), placebo, or medical device(s) intended to be administered to a study participant according to the study protocol.

### **6.1. Study Intervention(s) Administered**

Participants will receive saline and SP by intradermal injection, and histamine by skin prick.

Saline and histamine will be sourced by the site; histamine will be administered in accordance with manufacturer's instructions.

SP drug substance will be supplied by GSK and prepared into drug product extemporaneously at the trial site prior to administration.

Intervention Name	Substance P
Type	Drug
Formulation	Solution for injection
Unit Strength(s)	3.0, 1.0, 0.3 and 0.1 $\mu$ mol/L (with possible increase up to 10 $\mu$ mol/L, if no wheal and flare response is observed)
Dosage Level(s)	50 $\mu$ L of: 150, 50, 15 and 5 pmol (with possible increase up to 500 pmol if no wheal and flare response is observed)
Route of Administration	Intradermal injection
Use	Challenge agent
Sourcing	Drug substance provided centrally by sponsor then prepared to drug product locally by the trial site.
Packaging and Labelling	Study Intervention will be provided in vials. Each vial will be labelled as required per country requirement.

## 6.2. Preparation/Handling/Storage/Accountability

1. The investigator or designee must confirm appropriate temperature conditions have been maintained during transit for all study intervention received and any discrepancies are reported and resolved before use of the study intervention.
2. Only participants enrolled in the study may receive study intervention and only authorized site staff may supply or administer study intervention. All study interventions must be stored in a secure, environmentally controlled, and monitored (manual or automated) area in accordance with the labeled storage conditions with access limited to the investigator and authorized site staff.
3. The investigator, institution, or the head of the medical institution (where applicable) is responsible for study intervention accountability, reconciliation, and record maintenance (i.e., receipt, reconciliation, and final disposition records).
4. Further guidance and information for the final disposition of unused study intervention are provided in the Pharmacy Manual.
5. Information on the biomarker sampling device can be found in the Study Reference Manual (SRM)
- Under normal conditions of handling and administration, study intervention is not expected to pose significant safety risks to site staff. Take adequate precautions to avoid direct eye or skin contact and the generation of aerosols or mists. In the case of unintentional occupational exposure notify the monitor, Medical Monitor and/or GSK study contact.

- A Material Safety Data Sheet (MSDS)/equivalent document describing occupational hazards and recommended handling precautions either will be provided to the investigator, where this is required by local laws, or is available upon request from GSK.

### **6.3. Measures to Minimize Bias: Randomization and Blinding**

Not applicable.

### **6.4. Study Intervention Compliance**

- When the individual SP concentration for a participant is prepared from a bulk supply, the preparation will be confirmed by a second member of the study site staff.
- When participants are administered SP at the site, they will receive study intervention directly from the investigator or designee, under medical supervision. The date and time of each administration in the clinic will be recorded in the source documents. The concentration of study intervention and study participant identification will be confirmed at the time of administration by a member of the study site staff other than the person administering the study intervention.

### **6.5. Modification of Substance P concentrations**

Following data reviews at the data review committee (DRC) (see Section [10.1.5](#)) in Part 1, higher/lower concentrations of SP might be administered to subsequent participants, depending on the wheal reactions observed (see Section [4.3](#)). The maximum amount of SP administered in a single injection will not exceed 50  $\mu$ L of 10  $\mu$ mol/L, and up to a maximum of 10 injections of SP will be allowed per challenge visit.

### **6.6. Intervention after the End of the Study**

There will be no intervention offered at the end of the study.

### **6.7. Treatment of Overdose**

- Intradermal SP doses up to ~7.5-fold higher than those planned for this study and up to ~2.3-fold higher than those permitted in this study have been reported to show no important side effects [Grouzmann, 2011; Zirbs, 2013], and thus an overdose is not anticipated given the use and local delivery. In case of any overexposure to SP refer to the MSDS.
- Histamine dose selection is based on the product label for histamine injection as a positive skin test control. An overdose is not anticipated given the per-product label use and local delivery, refer to the product label.

In case of any overexposure or evidence of systemic adverse reactions to histamine, please refer to the product label for appropriate treatment response including, but not limited to tourniquet application, epinephrine administration, and antihistamine administration.

In the event of an overdose, the investigator should:

1. Contact the Medical Monitor immediately.
2. Closely monitor the participant for AE/SAE and laboratory abnormalities until stable or resolved.
3. Document the quantity of the excess concentration as well as the duration of the overdosing in the CRF.

Decisions regarding dose interruptions or modifications will be made by the investigator in consultation with the Medical Monitor based on the clinical evaluation of the participant.

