### 2.3.1. Risk Assessment

Potential Risk of Clinical Significance	Summary of Data/Rationale for Risk	Mitigation Strategy
Intradermal Substance P (SP) Challenge Agent		
Substance P intradermal challenge	
Transient local and limited regional skin flushing and local urticarial-like oedema has been observed with intradermal administration. One study with total doses of 5575 pmol intradermally in a single day had no systemic effects noted [Zirbs, 2013]. A second study administered a total dose of 5555 pmol [Grouzmann, 2011] with only minor flushing and no blood pressure effects.
 
Transient flushing, tachycardia, dizziness, and decreased blood pressure have been observed with intravenous dosing at >16 pmol/min for 6 minutes (96 pmol). [Newby, 1997].
	
Only small doses of Substance P will be administered intradermally. For Part 1 the planned doses will total 220 pmol and Part 2 the planned doses will total 740 pmol resulting in a 25x and 7.5x coverage from the previously safe doses administered in reported publications [Zirbs, 2013; Grouzmann, 2011].
 
There is a provision to administer up to 500 pmol should no wheal and flare occur at lower doses. This top allowed dose would result in a Part 1 total dose of 715 pmol and a Part 2 total dose of 2430 pmol, still resulting in a 7.8x and 2.3x coverage from the previously safe doses administered in reported publications [Zirbs, 2013; Grouzmann, 2011].
 
The participants will be closely monitored during administration of SP challenge. The clinical site will have appropriate precautions and treatments in place during

Potential Risk of Clinical Significance	Summary of Data/Rationale for Risk	Mitigation Strategy
		administration and post-administration observation.
Skin prick test-Histamine Control Agent		

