#### **4.3. Justification for Substance P concentrations**

Published data indicate that the wheal and flare responses to intradermal SP continue to increase with increasing concentrations, even up to 100  $\mu\text{mol/L}$  [Zirbs, 2013]. However, at the cellular level in an in-vitro mast cell line, SP begins to exert effects at  $\sim 0.1 \mu\text{mol/L}$  and the effect plateaus at  $\sim 10 \mu\text{mol/L}$ . The probable reason for the result in human skin is as the concentration of SP increases, it diffuses to a larger area of the dermis, causing larger reactions by activating more mast cells. To avoid concentrations of SP that are well above maximum effectiveness, the human mast cell line data were used to determine the SP concentrations in this study. Concentrations of 0.1, 0.3, 1 and 3  $\mu\text{mol/L}$  SP are expected to give a range up to  $\sim 95\%$  of the maximum effect at the cellular level. Those concentrations have been shown to cause wheal and flare responses when given intradermally to healthy people [Borici-Mazi, 1999; Grouzmann, 2011; Sabroe, 1997; Zirbs, 2013].

To allow for possible differences between published data and our SP challenge model, the concentrations of SP may be changed during the study in order to elicit the desired wheal response. For example, if the wheal response following one or more SP concentrations was indistinguishable from the wheal response following saline, and/or the wheal response was indistinguishable between 2 concentrations of SP, the concentrations could be adjusted accordingly. The maximum amount of SP administered in a single injection will not exceed 50  $\mu\text{L}$  of 10  $\mu\text{mol/L}$ .

The SP concentrations administered in Part 2 will be selected to ensure that the lowest concentration gives a wheal response larger than the wheal response following saline, and that each increasing concentration gives a wheal response larger than that at the previous concentration.

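### The coverage factors of 7.8x and 2.3x describe one concentration series, not the doses that Sections 4.3 and 6.5 of the protocol permit

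*Protocol*

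**What the plan says.** Protocol Section 6.7 gives two margins: about 7.5-fold over the planned doses, and published doses "up to ~2.3-fold higher than those permitted in this study". From these it concludes that an overdose is not anticipated.

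Section 2.3.1 supplies the totals. For the planned series, "For Part 1 the planned doses will total 220 pmol and Part 2 the planned doses will total 740 pmol". For the provision to go up to 500 pmol per injection, "This top allowed dose would result in a Part 1 total dose of 715 pmol and a Part 2 total dose of 2430 pmol", with coverage put at 7.8x and 2.3x. The comparators are two published studies: "One study with total doses of 5575 pmol intradermally in a single day had no systemic effects noted" and "A second study administered a total dose of 5555 pmol".

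The limits themselves are in Sections 4.3 and 6.5. One injection may not exceed 50 µL of 10 µmol/L, and "up to a maximum of 10 injections of SP will be allowed per challenge visit". Concentrations may be changed during the study. One of the examples in Section 4.3 is that if "the wheal response was indistinguishable between 2 concentrations of SP, the concentrations could be adjusted accordingly". Under Sections 6.5 and 10.1.5 the data review committee makes these changes.

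**The concern.** Section 6.7 sets *planned* against *permitted* doses, so a reader takes 2.3-fold as the smallest margin the protocol allows. Section 2.3.1 supports that reading by treating the visit total as a consequence of the top dose. A top dose does not fix a total, because the total also depends on the three lower concentrations and on the concentration used for the biopsy injections. Neither the protocol nor the SAP states a total per visit or a rule for spacing the concentrations.

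The coverage factors are the main quantitative mitigation in the Substance P row of the risk table, and Section 6.7 relies on them again. A review committee could choose a series that respects every stated limit and exceeds the total behind the claimed coverage, while the protocol still said 7.8x and 2.3x.

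This could arise in practice. Section 4.3 requires the lowest Part 2 concentration to give a larger wheal than saline. If low concentrations fail, the bottom of the series may be raised while the top stays capped at 10 µmol/L, which compresses a four-step series upwards.

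**Working it through.** **Inputs**
- Published totals: 5575 and 5555 pmol (Section 2.3.1). I use 5555, the smaller.
- Planned doses per 50 µL injection: "150, 50, 15 and 5 pmol" (Section 6.1).
- Cap per injection: 50 µL × 10 µmol/L = 500 pmol (Sections 4.3 and 6.5).
- Part 1: up to four injections. Part 2: up to four concentrations in duplicate, plus up to two more at one concentration if biopsies are done (Section 1.3.2). Section 4.1 places the biopsy injections at Challenge Visit 2.

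**Formulas**
- Dose (pmol) = concentration (µmol/L) × 50.
- Part 1 total = S, the sum of the doses in the series.
- Part 2 total = 2S without biopsy injections, or 2S + 2B with them, where B is the dose per biopsy injection.
- Coverage = 5555 / total.

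**The protocol's own figures**
- Planned series 5/15/50/150 pmol: S = 220 and 5555/220 = 25.3. With B = 150, 2 × 220 + 2 × 150 = 740 and 5555/740 = 7.5.
- Series 15/50/150/500 pmol (0.3/1/3/10 µmol/L): S = 715 and 5555/715 = 7.8. With B = 500, 2 × 715 + 2 × 500 = 2430 and 5555/2430 = 2.29.

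All four totals and all four factors reproduce. The Part 2 totals do so with both biopsy injections at the top concentration.

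**Other series within the stated limits**

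These two series are my illustrations, not figures from the documents. Each is ascending and stops at 10 µmol/L.

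| Series (µmol/L) | Part 1 | Part 2, no biopsy injections | Part 2 Visit 2, two biopsy injections at 10 µmol/L |
|---|---|---|---|
| 0.3/1/3/10 (protocol) | 715 pmol, 7.8x | 1430 pmol, 3.9x | 2430 pmol, 2.3x |
| 1.25/2.5/5/10 | 937.5 pmol, 5.9x | 1875 pmol, 3.0x | 2875 pmol, 1.9x |
| 2.5/5/7.5/10 | 1250 pmol, 4.4x | 2500 pmol, 2.2x | 3500 pmol, 1.6x |

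For the second row, S = 62.5 + 125 + 250 + 500 = 937.5, and 2 × 937.5 + 2 × 500 = 2875. For the third, S = 125 + 250 + 375 + 500 = 1250, and 2 × 1250 + 2 × 500 = 3500.

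In a four-step series with 10 µmol/L at the top and biopsies taken there, raising any lower step above 0.3, 1 or 3 without lowering another takes the total above 2430 pmol.

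**The case against.** **The arithmetic is right.** This stands. Every stated total and ratio reproduces, and only the scope given to the ratios is in question.

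**The limits do not allow a margin as low as 1.1-fold.** A reader might infer otherwise from Section 6.5 alone: 10 × 500 = 5000 pmol, and 5555/5000 = 1.11. Likewise four injections at the cap in Part 1 give 2000 pmol, or 2.8-fold. Both need equal injections at the cap. Section 4.1 requires different concentrations given from lowest to highest, and Section 4.3 requires each Part 2 step to give a larger wheal than the one before. These figures are therefore bounds that a compliant series cannot reach. Tightly packed series near 10 µmol/L also fit poorly with the aim in Section 4.3 of avoiding concentrations well above maximum effectiveness.

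**Falling below 2.3 depends largely on an optional component.** This stands in part. Biopsies may not be done, and Figure 2 specifies only one of the SP concentrations for these injections, not the top one. For 1.25/2.5/5/10, biopsy injections at 5 µmol/L give 1875 + 2 × 250 = 2375 pmol, or 2.34-fold, and omitting them gives 3.0-fold. However, the protocol's own 2430 pmol includes them at the top concentration, so that is the like-for-like comparison. The series 2.5/5/7.5/10 gives 2.2-fold even without them, only slightly below the stated figure.

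**The increase to 500 pmol is conditional.** Sections 2.3.1 and 6.1 tie it to an absence of wheal and flare response. Sections 4.3 and 6.5 are broader, and the condition governs use of the top dose without fixing the lower steps.

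**Exceeding 2430 pmol is not inevitable.** A failing step could be dropped, since up to four concentrations are allowed. For example, 1/3/10 gives 2 × 700 + 2 × 500 = 2400 pmol, or 2.3-fold.

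**A limit may exist elsewhere.** SAP Section 4.7 says that data reviews follow a Dose Escalation Plan, which was not available. It may cap the total. If so, the protocol sections that claim the margin neither state the cap nor cite that plan.

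**Conclusion.** The inconsistency holds. The 7.8x and 2.3x are correct for 0.3/1/3/10 µmol/L, in Part 2 given in duplicate with two biopsy injections at 10 µmol/L. They are not the minimum coverage over the doses that Sections 4.3 and 6.5 permit.

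On the two illustrative series, Part 2 coverage at Visit 2 falls to between 1.9-fold and 1.6-fold, assuming both biopsy injections are given at the top concentration. Part 1 coverage falls to between 5.9-fold and 4.4-fold. The exact values depend on the series assumed.

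A reader might also infer that permitted doses could exceed those in the published studies. They could not: even the unreachable 5000 pmol is below 5555 pmol. The direction of the statement in Section 6.7 therefore survives, and the size of the margin does not. The conclusion rests on the protocol and SAP alone, and a cap in the Dose Escalation Plan would narrow it to a missing cross-reference.

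**What to change.** Reconcile Sections 2.3.1, 4.3, 6.5 and 6.7 so that the coverage factors and the permitted doses refer to the same totals. One way is to state the series and the biopsy assumption behind 7.8x and 2.3x, and to give beside them the minimum coverage that the permitted limits imply. If the Dose Escalation Plan already limits the visit total, cite it where the margin is claimed. Which limit applies is for the sponsor to decide, and nothing here proposes one.

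The cost is wording in four protocol sections. If the present limits stand, the stated margin becomes less favourable.

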## **6.8. Concomitant Therapy**

Any medication or vaccine (including over-the-counter or prescription medicines, vitamins, and/or herbal supplements that the participant is receiving at the time of enrolment or receives during the study must be recorded along with:

- reason for use
- dates of administration including start and end dates
- dosage information including dose and frequency

The Medical Monitor should be contacted if there are any questions regarding concomitant or prior therapy.

Participants must abstain from taking prescription or non-prescription drugs (including vitamins and dietary or herbal supplements) within 7 days (or 14 days if the drug is a potential enzyme inducer) or 5 half-lives (whichever is longer) before the start of study intervention until completion of the last visit, unless, in the opinion of the investigator and sponsor, the medication will not interfere with the study.

Paracetamol, at doses of  $\leq$  2 grams/day, is permitted for use any time during the study.

Other concomitant medication may be considered on a case-by-case basis by the investigator in consultation with the Medical Monitor if required.

## **7. DISCONTINUATION OF STUDY INTERVENTION AND PARTICIPANT DISCONTINUATION/WITHDRAWAL**

### **7.1. Study Stopping criteria**

- If a SAE, considered reasonably attributable to study intervention (SP, histamine) in the opinion of the Investigator, occurs in one participant, then dosing will be temporarily halted, and no further participants will be enrolled or dosed until a full safety review of the data has taken place. Relevant reporting and discussion with the Medical Monitor, relevant site personnel, and the IRB/IEC will take place before resumption of enrolment or dosing.

- If the significant clinical or laboratory abnormality, considered reasonably attributable to study intervention (SP, histamine) in the opinion of the Investigator, occurs in more than 2 participants, then dosing will be temporarily halted, and no further participants will be enrolled or dosed until a full safety review of the data has taken place. Relevant reporting and discussion with the Medical Monitor, relevant site personnel, and the IRB/IEC will take place before resumption of enrolment or dosing.

